1.8. Variables and Instruments

Feasibility. Feasibility will be assessed by examining (a) study accrual of Black and Hispanic breast cancer patients (N=60 over 9 months), (b) protocol adherence ($>80\%$ adherence to the protocol [defined in this study as the degree to which participants are willing and able to complete the intervention exposure], e.g., TOLF, e-Lymph, and (c) participant retention ($>80\%$ data collected at the study appointment, including pre-randomization (A1-Week 0) and post-assessments (A2- Week 9 and A3- Week 13). **Acceptability.** Acceptability will be assessed post-intervention using the validated scale of patient satisfaction and acceptability and exit interview.⁶⁰

Primary and Secondary Outcomes. Lymphatic Pain: The Breast Cancer and Lymphedema Symptom Experience Index (BCLE-SEI) Part I, a reliable and valid self-report instrument,^{54,61-63} is used to assess self-reported lymphatic pain.^{2-3,13,64} The items are rated on a Likert scale from 0 (no lymphatic pain/swelling) to 4 (greatest severity of lymphatic pain/swelling). Pain Severity and Interference: are measured using the Brief Pain Inventory-Short Form (BPI-SF) with demonstrated reliability and validity.⁶⁵ The BPI-SF consists of four items assessing pain severity (worst, least, average, and current pain) and seven items assessing pain interference in the past week. Lymph Fluid Level by Bioimpedance: The Imp XCA® (Impedimed, Brisbane, Australia), a bioelectrical impedance analysis (BIA) device is used to assess lymph fluid level. The device measures the resistance of the extracellular fluid (i.e. the impedance) in terms of the L-Dex ratio, taking into consideration the ratio between the dominant and non-dominant arms.⁶⁶⁻⁶⁷ Daily Living Function: Daily living function is operationalized as Activities of Daily Living (ADLs) that reflect the real-world daily living of breast cancer patients. The 13-item subscale of ADLs in BCLE-SEI Part II is used to assess self-reported difficulty in performing thirteen ADLs.^{2,38} Cronbach's alpha for the ADLs subscale is 0.94.^{2,38} Psychological Distress. The 12-item subscale of psychological/emotional distress subscale from the BCLE-SEI Part II is used to assess the distress of being frustrated, sad, guilt/self-blame, worried, irritable, fearful, angry, lonely, helpless, hopeless, anxious, and depressed. Cronbach's alpha for the psychological/emotional distress subscale was 0.91.^{62,64} Quality of Life. The 10-item V1.2 Patient Reported Outcome Measure Information System Global Health Scale (PROMIS GHS), ($\alpha = 0.80-0.86$)⁶⁸ that captures self-perception of QOL on a scale from 1 (poor), 2 (fair), 3 (good), 4 (very good) to 5 (excellent). Self-efficacy for Pain Management. The 5-item Chronic Pain Self-Efficacy Scale⁸¹ with good reliability⁶⁹⁻⁷⁰ is used

to assess patients' certainty about their degree of pain control, pain during daily activities, controlling pain during sleep, and making pain reductions without extra medication.

Potential Covariate Variables. *Socioeconomic Determinants of Health.* Items to screen for social needs and financial strains in The Accountable Health Communities (AHC) model⁷¹⁻⁷⁶ are used to assess socioeconomic determinants: (1) 2-item for living situation, (2) 2-item for food, (3) 1-item for transportation, (4) 1-item for utilities, (5) 4-item for safety, and (6) 1-item for financial strain. *Medical and Demographic Information.* Demographic data includes age, race, marital status, education, income. Patients will provide information on ethnicity, marital status, and education. Participants' electronic medical record will provide initial and/or recurrent diagnosis date, disease stage, cancer treatments (i.e., chemotherapy, radiation, surgery history/type), medical comorbidities, height and weight, and use of antidepressant, anxiolytics, and pain medications.

1.9.a. Data Collection Schedule and Procedures.

Data Collection. Participants in Phase II/Aim 2 RCT will have three in-person research visits to complete study assessment measures pre-randomization (A1-Week 0), post-intervention assessment measure (A2-Week 9 and A3-Week 13). Data collection during each in-person visit will take approximately 30 minutes.

Data Recording. All participants will be assigned a unique study identification number to ensure confidentiality. Demographic and cancer treatment related data, will be recorded directly into the computer database. Bioimpedance data are recorded directly into the computer database. Field notes at each data collection point will be digitally-recorded and transcribed for data coding and summary. **Data Storage.** Data will be stored in locked files accessible only to the research team. Electronic data will be stored in a password protected computer accessible only to the PI, Co-Investigators, and the research team members.

1.9.b. Data Analysis and Interpretations

Qualitative Data Analysis (Phase I/Aim 1). Qualitative data obtained from focus groups will be transcribed verbatim. We will use NVivo software to manage data and assist in data analysis. We will use a modified iterative descriptive data analysis method^{5,25-26,53,58} to ensure the credibility of data analysis. This iterative process will be used to examine data, compare codes, challenge interpretations, and develop themes inductively. Essential themes and descriptive summary will be produced and used to inform the intervention.

Statistical Analysis for Phase II/Aim 2. Sixty patients (N=60) will be randomized into two equal sized groups with 1:1 ratio, either to TOLF or e-Lymph group. *Feasibility* will be assessed by examining (a) study accrual of breast cancer patients (N=60 over 9 months), (b) protocol adherence (>80% adherence to the protocol [defined in this study as the degree to which participants are willing and able to complete the intervention exposure], e.g., TOLF or e-Lymph), and (c) participant retention (>80% data collected at the study appointments). *Acceptability* will be assessed post-intervention using the validated scale of patient satisfaction and acceptability and exit interview.⁷⁷ *Evidence of Promising Outcomes.* Assuming a minimum protocol adherence of 80%, there will be at least 48 participants who will rate whether treatment is acceptable. Assuming acceptability is 50% which has the most conservative precision interval, the acceptability will be estimated within 8%.

Primary Endpoint. The primary endpoint is the complete reduction of lymphatic pain and reduced pain severity and interference reported by participants, and reduced lymph fluid level at week 13 post intervention.

Statistical Analysis for Outcomes. We hypothesize that participants who receive the TOLF will have better primary and secondary outcomes than participants who receive the control e-Lymph over time. Since outcomes will be measured at week 0 (baseline), 9 weeks and 13 weeks post intervention, generalized estimating equation (GEE) model will be used for analyzing each outcome to accommodate the correlation among the repeated measurements within a same subject.⁷⁸ Different working correlation matrices will be tested to select the most appropriate one for the GEE models. Identity link and logit link will be used for continuous outcomes (lymphatic pain severity, pain severity and interference, lymph fluid level, daily living

function, psychological distress, QOL, and self-efficacy for pain management) and binary outcome (complete pain reduction), respectively. The predictors include two indicators of intervention and control groups respectively. Covariates found to be significantly different between the groups at baseline, will be included in the GEE model.⁷⁹ If the primary outcomes of the intervention group are significant at alpha 0.05, we will conclude the intervention works better than the control. Proper methods will be used to address any missing data to maximize the statistical power of our analyses and reduces the likelihood of systematic bias in estimates.

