Behavioral Interventions Are Efficacious in Treating Lymphatic Pain. Lymphatic pain is associated with increased lymph fluid accumulation,^{2,4} and inflammatory responses.³⁹⁻⁴¹ Limited research tested integrative behavioral interventions based on physiological (lymph fluid accumulation and inflammation) and cognitive principles (low self-efficacy). We have developed and extensively tested a non-pharmacological, behavioral *The-Optimal-Lymph-Flow* (TOLF) intervention that includes strategies to promote lymph flow: therapeutic lymphatic exercises, healthy diet (i.e., nutrition-balanced, portion-appropriate diet, adequate hydration), and proper sleep.¹³⁻²¹ The core TOLF intervention is 8-minute TOLF lymphatic exercises to promote lymph flow (i.e., muscle-tightening deep breathing, muscle-tightening pumping, and limb mobility exercises).¹³ TOLF includes a website that provides patients with TOLF intervention materials, information, and daily assessments used to personalize sessions.¹³⁻²¹ One dose of TOLF lymphatic exercises can produce immediate significant effects on reductions in pain, swelling, and reduction in lymph fluid levels.¹³ Our recent publish RCT demonstrated that 50% of patients who received TOLF intervention achieved a complete pain reduction (50% vs 22%; OR=3.56, CI = [1.39, 9.76], p=0.005) compared to control of 22%.¹⁴ Given TOLF is efficacious, focusing on self-management skills, having immediate therapeutic effects, and welcomed by patients (only 6% attrition), TOLF may provide particular benefits for Black and Hispanic patients who face personal challenges of time, travel, competing demands, cost for therapist-administered treatment. In addition, technologically-driven delivery model makes it easy for community-level implementation to address system barriers of intervention availability, staffing, therapist.

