In Phase II RCT, a total of 60 participants will be recruited consisting of 30 Black and 30 Hispanic patient participants, respectively. Following baseline assessment, 30 Black and 30 Hispanic patient participants will be randomly assigned with equal allocation to one of two conditions: 1) TOLF (Intervention), or 2) e-Lymph (Control). e-Lymph includes training sessions on the lymphatic system, lymphedema, lymphedema diagnosis and measurement, risk of lymphedema. The major goals of skill training sessions for TOLF and e-Lymph are described in **Table 1**. Randomization will be blocked by ethnicity to ensure reasonable balance in each treatment condition. The data manager on this study who is not involved with recruitment will randomly draw a number of 1, or 2 to be given the participant's study number (not name) to randomize the participant. Our research evaluator will not

Patient Sessions	The-Optimal-Lymph-Flow (TOLF)	Lymphedema Education (e-Lymph)
1 In-person (40 minutes)	
 In-person learning the Importance of promoting lymph flow In-person training and practicing lymphatic exercises using Kinect-TOLF Learning on lymphatic system, lymphedema, lymphedema diagnosis and measurements Home practice planning 	
 In-person learning on lymphatic system, lymphedema, lymphedema diagnosis and measurements
2 Virtual (20 minutes)	
 Home practice review Learning the importance of large muscle exercises to promote lymph flow Home practice planning for large muscle exercises (e.g., walking, running, dancing, yoga) 3 times per week for 30 minutes Home practice planning 	
 Home review Questions and Answers
3 Virtual (20 minutes)	
 Home practice review Learning the importance of weight for lymph flow Planning for healthy diet and sleep hygiene Home practice planning 	
 Home review Questions and Answers
4 Virtual (20 minutes)	
 Home practice review Planning for maintenance of all learned skills 	
 Home review Questions and Answers

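### Could the >80% retention criterion be met with too few women assessed at week 13, since it lists the baseline visit and gives no pooling rule?

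*Combined protocol and SAP*

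**What the plan says.** Section 1.8 (Feasibility) names retention as one of three feasibility measures. The target is more than 80% of "data collected at the study appointment, including pre-randomization (A1-Week 0) and post-assessments (A2- Week 9 and A3- Week 13". Section 1.9.b repeats it more briefly as "participant retention (>80% data collected at the study appointments", naming no visit.

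The surrounding facts are clear:

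- Section 1.9.b gives the sample: "Sixty patients (N=60) will be randomized into two equal sized groups with 1:1 ratio".
- Section 1.7 places randomisation after the first assessment: "Following baseline assessment, 30 Black and 30 Hispanic patient participants will be randomly assigned with equal allocation to one of two conditions".
- Section 1.9.a schedules "three in-person research visits to complete study assessment measures pre-randomization (A1-Week 0), post-intervention assessment measure (A2-Week 9 and A3-Week 13".
- Section 1.9.b puts the primary endpoint at the last of these, ending with "reduced lymph fluid level at week 13 post intervention".

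Neither statement of the criterion says whether the percentage is pooled or per visit, what the denominator is, or whether it is to be shown by arm. Neither says what follows if the target is missed.

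**The concern.** Retention should describe who stays after randomisation. A woman cannot be randomised here until she has been assessed at baseline, so among randomised women the A1 visit is attended almost by definition. Putting it in a pooled percentage adds 60 near-certain successes. Pooling has a second effect: good attendance at week 9 can offset poor attendance at week 13, where the primary endpoint lies.

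Feasibility comes first among the purposes of Aim 2. If the same attendance data can pass on one reading and fail on the other, the reading could be chosen after the data are seen. A later trial could then be planned on a reported retention above 80% when fewer than 80% of women were assessed at the time point that matters. The plan's statement on missing data is general and sets no separate limit on loss at week 13.

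**Working it through.** The plan derives no retention figure, so there is nothing to reproduce. The check is a direct count.

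**Inputs.** 60 randomised (1.9.b); three assessments, at weeks 0, 9 and 13 (1.9.a); threshold above 80% (1.8 and 1.9.b). Assumptions: the denominator is the 60 randomised, A1 is 60/60, and a woman missing at week 9 is also missing at week 13, so A3 ≤ A2.

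**Per visit.** 0.80 × 60 = 48, so passing needs at least 49/60 = 81.7% at each visit, week 13 included. A1 passes automatically and changes nothing.

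**Pooled over three visits.** 60 × 3 = 180 and 0.80 × 180 = 144, so passing needs 145. Subtracting A1: 145 − 60 = 85 of 120 follow-up assessments = 70.8%.

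- A2 = 43, A3 = 42: week 13 at 70.0%.
- A2 = 50, A3 = 35: week 13 at 58.3%.
- A2 = 60, A3 = 25: week 13 at 41.7%. This is the arithmetic floor. It requires no loss by week 9 and then 35 of 60 women lost in four weeks, which is not credible.

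**Pooled over A2 and A3 only.** 0.80 × 120 = 96, so passing needs 97. With A2 = 60, A3 = 37 = 61.7%. Removing baseline alone would therefore not close the gap.

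**A moderate case (assumed attendance).** A2 = 52, A3 = 45:

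| Reading | Count | Result |
|---|---|---|
| Pooled, with A1 | 157/180 | 87.2%, pass |
| Pooled, without A1 | 97/120 | 80.8%, pass |
| Week 13 alone | 45/60 | 75.0%, fail |

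The verdict here turns on pooling. Whether A1 is counted makes no difference to it.

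**Where the readings disagree.** Let follow-up attendance be the same number x at both visits. Pooled over three visits, 60 + 2x must exceed 144, so x ≥ 43. Per visit, x ≥ 49. The verdicts differ only for x from 43 to 48 (71.7% to 80.0%).

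**Chance of passing.** Assume each woman independently attends both follow-up visits or neither. The binomial probabilities are:

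| True retention | Pooled, three visits | Per visit |
|---|---|---|
| 70% | 0.451 | 0.029 |
| 75% | 0.775 | 0.148 |
| 80% | 0.957 | 0.449 |

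**At the attrition the plan cites.** Section 1.4 describes TOLF as "welcomed by patients (only 6% attrition". Then 60 × 0.94 = 56.4, about 56 women. Per visit this is 56/60 = 93.3%; pooled over three visits it is (60 + 56 + 56)/180 = 95.6%. Every reading passes. The figure comes from earlier work, and section 1.1 says that TOLF was tested in largely White patients, so it is only indicative.

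**The case for a change.** The best argument for acting is that the gap is real and cheap to close. The two sections give no rule, and the arithmetic above is not in dispute. All assessments are in person, in a population for whom the plan itself expects practical obstacles to attending, so retention in the 70s is possible. In that range the choice of reading decides the verdict. One sentence in each section would settle it.

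That much stands: the wording is incomplete. The step from incomplete to lax does not.

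- **No passage mentions a total or an average over visits.** Section 1.8 uses the singular for the appointment and then lists the three visits, which fits a target at each one. The plural in section 1.9.b fits either reading.
- **Listing A1 has a sensible purpose.** The criterion concerns data collected, not attendance alone. A woman can attend baseline and still lack a questionnaire or a bioimpedance reading, and the planned GEE uses week 0 as well as weeks 9 and 13. Section 1.7 speaks of 60 recruited before it describes randomisation, so if the count starts at recruitment, A1 could fall below 60/60.
- **Nothing is triggered by the figure.** The plan examines retention. It attaches no progression rule to it, and the outcome analysis does not use it.

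The obvious repair also has a cost. Moving the target to week 13 alone would, on the per-visit reading, remove the requirement that now applies at week 9. Counting women with primary outcome data would raise a new question, because the primary endpoint combines lymphatic pain, pain severity and interference, and lymph fluid level. Reporting by arm is good practice, but its absence here contradicts nothing in the plan.

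**Conclusion.** No change to the plan follows. The concern correctly identifies an unstated rule and denominator, but the harm arises only on a pooled reading that the documents never adopt. Read visit by visit, the criterion already demands 49 of 60 at week 13, and the baseline entry is harmless. A statistician reporting this pilot would give the number assessed at each visit out of those randomised, and readers would then see week-13 retention directly, whatever summary percentage accompanied it.

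If the pooled reading were nevertheless used, the effect would be a pass at 43 to 48 of 60 where the per-visit reading fails, assuming equal attendance at both follow-up visits. Unequal attendance widens that range, but the 25-of-60 floor is not a realistic case. These counts assume 60 randomised women, complete baseline assessment and no return after dropout. The conclusion also rests on the absence of any decision rule tied to retention. If progression to a larger trial were made to depend on this figure, the definition would need to be written down first.

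### The acceptability precision of 8% with 48 raters has no confidence level and is too narrow: at 95% the margin is about 14 percentage points

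*Combined protocol and SAP*

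**What the plan says.** The statement is in Section 1.9.b, under Statistical Analysis for Phase II/Aim 2. The design is given first: "Sixty patients (N=60) will be randomized into two equal sized groups with 1:1 ratio, either to TOLF or e-Lymph group". The number of raters is then projected from adherence: "Assuming a minimum protocol adherence of 80%, there will be at least 48 participants who will rate whether treatment is acceptable". The precision follows in the next sentence: "Assuming acceptability is 50% which has the most conservative precision interval, the acceptability will be estimated within 8"%.

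Neither that section nor any other part of the document supplied gives a confidence level, a formula or an interval method for this figure. The only error rate in the plan applies to the efficacy outcomes, also in Section 1.9.b: "If the primary outcomes of the intervention group are significant at alpha 0.05, we will conclude the intervention works better than the control".

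Section 1.8 describes the measurement: "Acceptability will be assessed post-intervention using the validated scale of patient satisfaction and acceptability and exit interview".

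**The concern.** A margin of error has no meaning without a confidence level, and here the inputs are stated, so the margin can be checked. Eight points looks too small for 48 binary ratings.

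Acceptability is one of the things Aim 2 sets out to examine, and this sentence is where the analysis section says how well it will be known. The sentence also presents 50% as the worst case, so a reader will take 8 points as an upper bound on the uncertainty. That reader would expect a result of 50% to come with an interval of roughly 42% to 58%. If the usual 95% level applies, the interval would run from about 35% to 65%.

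**Working it through.** **Inputs (all from Section 1.9.b)**

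- Randomised: 60, in two equal arms.
- Raters: 0.80 × 60 = 48.
- Assumed acceptability: p = 0.50.
- Stated precision: 8%.
- Confidence level: not stated, so a range is shown.

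**Attempt to reproduce the stated figure**

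Half-width = z × √(p(1 − p)/n). The standard error is √(0.25/48) = 0.0722, or 7.2 points.

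| Two-sided level | z | Half-width, n = 48 |
|---|---|---|
| 80% | 1.2816 | 9.2 points |
| 90% | 1.6449 | 11.9 points |
| 95% | 1.9600 | 14.1 points |
| 99% | 2.5758 | 18.6 points |

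None of these gives 8.

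**Confidence level implied by 8 points**

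0.08/0.0722 = 1.109 standard errors, and 2Φ(1.109) − 1 = 0.732, or about 73%. If 8 is a rounding of anything from 7.5 to 8.5, the implied level runs from about 70% to 76%.

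**Other readings tried**

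- Other 95% methods with 24 of 48 rating the programme acceptable: Wilson 36.4% to 63.6% (half-width 13.6), exact Clopper-Pearson 35.2% to 64.8% (14.8), continuity-corrected 15.2.
- One standard error: 7.2 points, which rounds to 7.
- All 60 women rating: standard error √(0.25/60) = 0.0645, so the half-width is 8.3 points at 80% and 12.7 at 95%.
- Finite-population correction for 60 women: 14.1 × √(12/59) = 6.4 points at 95%.
- A proportion other than 50%: at 95% with 48 raters the half-width is 8.5 points at p = 0.90 and 7.7 at p = 0.92. Eight points would therefore fit an acceptability just above 90%, but the sentence specifies 50%.
- Eight points as the full width: the half-width would be 4, which widens the gap.

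**Raters needed for 8 points at p = 0.50**

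n = z² × 0.25/0.08²: 64.2 at 80%, 105.7 at 90% and 150.06 at 95%. Rounded up, these are 65, 106 and 151. All exceed the 60 randomised.

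**Precision within one arm at 95%**

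With 24 raters: 1.96 × √(0.25/24) = 20.0 points. With all 30: 1.96 × √(0.25/30) = 17.9 points. The 24 assumes that 80% of an arm rates, which the plan does not state by arm.

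**The case against.** The best defence is that the plan never sets a confidence level for acceptability. The 0.05 alpha governs the efficacy outcomes, and its sidedness is not given, so 95% is the reviewer's choice. This is fair, and 14 points is conditional on that choice. It does not save the figure, because 8 points is also too narrow at 80% and 90%.

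A second defence is that 8% may be a mislabelled quantity. The plan says at least 48 raters, and all 60 women at 80% confidence would give 8.3 points, which rounds to 8. One standard error with 48 raters is 7.2, which is literally within 8. Either could be the origin of the number. But the first needs an unstated level and a number of raters that the calculation does not use, and the text does not describe the figure as a standard error. What stands is that the authors should be free to declare the level they meant.

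A third point is that little depends on the sentence. The feasibility criteria (accrual, adherence, retention) do not use it, there is no acceptability threshold, and the final interval will come from the data. This is correct and limits the seriousness.

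Finally, acceptability is measured with a satisfaction scale and an exit interview, and no cut-off is given that would turn these into a yes/no rate. A corrected margin still rests on that undefined proportion. This also stands, but it is a separate gap and does not make 8% right.

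**Conclusion.** The concern holds. The sentence gives no confidence level, and with its own inputs 8 points is not obtained at any usual level. At 95% the half-width is 14.1 points, about 1.8 times the stated figure (14.1/8). Having every randomised woman rate would still leave 12.7 points.

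The calculation takes acceptability as a simple proportion, pooled over both arms, with 48 independent ratings and p = 0.50. The 95% level is an assumption; the finding that 8 points is too narrow holds at 80% and above. The consequence is confined to a misleading planning statement. It should be corrected, but it does not affect the sample size or the efficacy analyses.

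**What to change.** In Section 1.9.b, replace the 8% by a margin of about 14 percentage points, stating that this is for a 95% confidence interval with 48 raters and both arms pooled, and name the interval method (Wilson or exact). If the authors intended another level, they should state it with the matching figure: 9.2 points at 80% or 11.9 at 90% with 48 raters.

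Two further clarifications are useful but not needed to close this point:

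- The 48 raters combine two different programmes, so acceptability should also be reported by arm, with the wider margin of about 18 to 20 points acknowledged.
- The number of raters is projected from adherence, so the plan should say that ratings are sought from every woman who attends the post-intervention assessment, whatever her adherence.

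The cost is one corrected sentence with a less favourable figure, one descriptive table if results are shown by arm, and one line on who rates. No extra patients or visits are required.

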1.2 Research Significance

Lymphatic pain is a cardinal sign for an early stage of lymphedema.³⁵⁻³⁷ Patients who report lymphatic pain are nearly twice as likely to develop lymphedema.⁴ Without timely intervention in this early stage, lymphedema can progress into a chronic condition that no surgical or medical interventions can cure.⁸ In addition, lymphatic pain and lymphedema significantly impact patients' daily living function,^{2,38-39} psychological distress,⁵ and QOL.⁴⁰⁻⁴¹ The burden from lymphatic pain and lymphedema and can be even higher for Black and Hispanic women. Studies show that women of racial minority background experience delays in breast cancer treatment and/or inadequate treatment.^{10-12;42-45} Later stage diagnosis and delayed treatment lead to high risk of lymphedema and pain due to the needs to have more aggressive surgical treatment, more lymph nodes removed, and radiation.⁹⁻¹² Further, women of minority are more likely to have comorbid health problems (e.g., obesity),^{2,11-12;25-28} the risk factor for lymphatic pain and lymphedema.^{3;31-34} Women with financial hardship are 4.64 times more likely to report lymphatic pain.² Our recently published study detailed that patients with lymphatic pain reported impairments in 45% of ADLs and had a significantly increased risk of having difficulty in performing all the 13 ADLs (i.e., cooking, using a knife, writing/typing, cleaning, vacuuming, laundry, carrying objects, yard work, dressing self, bathing self, driving, making bed, and taking care of children).² Patients' psychological distress was further compounded when they felt that clinicians did nothing but "pity me."⁵ Disparities among women with breast cancer in environmental justice communities are maintained by a lack of cost-effective, accessible, and appropriately adapted supportive care opportunities found at more resourced medical centers.⁴³⁻⁴⁴ This results in a large symptom burden (i.e., lymphatic pain,) for patients, providers, and healthcare systems.

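### Covariates enter the GEE only by a baseline significance test, so chance picks the model and no adjustment for the baseline value or ethnicity is prespecified

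*Combined protocol and SAP*

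**What the plan says.** Section 1.9.b (Statistical Analysis for Outcomes) plans one GEE per outcome. On the model terms it says "The predictors include two indicators of intervention and control groups respectively", and then "Covariates found to be significantly different between the groups at baseline, will be included in the GEE model". It gives no test, threshold or candidate list for that screen, and no other route by which a covariate can enter.

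On timing, the same section says "Since outcomes will be measured at week 0 (baseline), 9 weeks and 13 weeks post intervention", which makes week 0 a repeated response. The primary endpoint is placed at week 13, for example "reduced lymph fluid level at week 13 post intervention". The section names no time term, group-by-time term or baseline constraint.

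Section 1.8 (Potential Covariate Variables) lists social, demographic and medical items. The baseline values of the outcomes are not among them.

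Section 1.7 says "Randomization will be blocked by ethnicity to ensure reasonable balance in each treatment condition", with 30 Black and 30 Hispanic women allocated equally to the two arms. Ethnicity is not a stated model term.

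**The concern.** Under randomisation, any baseline difference between arms is due to chance. A significance screen therefore picks covariates by accident, whether or not they predict the outcome. The final model cannot be known until data by arm have been examined, and the analyst still has to choose the test, the threshold and the list.

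The baseline value of an outcome is usually the most useful covariate, and the plan does not fix how it is used. The blocking factor is balanced by design, so a test for imbalance will almost never select it.

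This matters even in a pilot. Section 1.9.b concludes in favour of the intervention from tests at 0.05, and the abstract presents the trial as a source of evidence on future efficacy. With 60 women, or 48 at the 80% retention limit, baseline information should not be wasted.

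**Working it through.** The plan gives no power, effect size or SD for the outcomes, so there is no stated figure to reproduce.

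**Inputs from the documents.** 60 women, 30 per arm; 80% retention, which gives 24 per arm; alpha 0.05; visits at weeks 0, 9 and 13.

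**Assumptions.** Two-sided tests; screening level 0.05; equal variances; effect 0.6 or 0.3 SD; between-visit correlation r = 0.3/0.5/0.7; linear-model (noncentral t) approximation to the GEE.

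**1. How often chance selects a covariate.** Section 1.8 yields about 20 candidates:
- 6 social-needs domains;
- 4 demographic items besides race or ethnicity;
- 10 medical items, with height and weight counted as BMI.

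Testing the 11 social-needs items singly gives 20 − 6 + 11 = 25. If candidates are independent, P(at least one flagged) = 1 − 0.95^20 = 64%, or 1 − 0.95^25 = 72%. Correlated candidates would give less.

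**2. Ethnicity.** A 15/15 split within each ethnic group gives p = 1.00. The procedure also says the data manager "will randomly draw a number of 1, or 2". If that draw were unrestricted, exact enumeration gives P(p < 0.05) = 5.2% (chi-square) or 2.7% (Fisher).

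**3. Three readings of how baseline is used (30 per arm).** The largest non-significant baseline gap is t(0.975, 58) × √(2/30) = 0.517 SD.

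(a) *Week-13 comparison, baseline value put through the screen.* Simulation (8,000 trials per setting) admits it in about 5% of trials. A gap just short of significance shifts the week-13 difference by r × 0.517 = 0.16/0.26/0.36 SD. Simulated null size is 4.6/4.1/3.4%.

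(b) *Unconstrained week-13-minus-week-0 contrast.* The gap is subtracted in full when only the fraction r should be. It is over-corrected by (1 − r) × 0.517 = 0.36/0.26/0.16 SD. The variance relative to baseline adjustment is 2(1 − r)/(1 − r²) = 1.54/1.33/1.18.

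(c) *Group indicators alone on all three visits.* The coefficient averages in the pre-randomisation visit. A 0.60 SD effect at both follow-up visits becomes 0.60 × 2/3 = 0.40 SD with exchangeable correlation, and 0.38/0.36/0.34 SD with AR(1).

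**4. Power at week 13.** Variance per woman is 1 for week 13 alone and 2(1 − r) for the contrast. For adjustment on baseline and ethnicity it is (1 − r²)(1 + 1/(N − 5)), with N − 4 degrees of freedom.

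| Per arm, effect | Week 13 alone | Contrast, r = 0.3/0.5/0.7 | Adjusted, r = 0.3/0.5/0.7 |
|---|---|---|---|
| 30, 0.6 SD | 63% | 49/63/84% | 66/74/89% |
| 24, 0.6 SD | 53% | 41/53/75% | 56/64/80% |
| 30, 0.3 SD | 21% | 16/21/31% | 22/26/35% |

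Under reading (a), simulated power with the screen at 0.6 SD and 30 per arm is 64/64/65%, barely above no adjustment. The 95% CI half-width at 30 per arm is 0.52 SD for week 13 alone, 0.61/0.52/0.40 for the contrast and 0.50/0.45/0.37 adjusted.

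**5. Complete pain reduction.** This uses 50% vs 22% (section 1.4), 30 per arm, and a latent-normal simulation of 4,000 trials that was not independently repeated. Power is 62–63% for the unadjusted risk difference and 65/70/79% for the standardised one. Null size is 4–6% and 5–6% respectively. The conditional odds ratio moves to about 4.2/5.1/7.5, while the standardised one stays at 3.6–3.7.

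**The case against.** The strongest reply is that week 0 is already in the GEE and that baseline outcomes are not listed as candidate covariates, so the plan may never screen them. This stands in part. Reading (a) is only one possibility, and its figures do not describe the plan as such. The losses under (b) and (c) come from unstated time and baseline terms rather than from the screening rule. The group indicators are also introduced as included predictors, not as a complete list, and the hypothesis refers to differences over time. But the text never says which reading applies, and that choice decides the estimate.

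Three stronger readings are tempting and should not be drawn:
- A reader might infer that every gap up to 0.52 SD goes unadjusted. That holds only under reading (a). Under (b) the gap is over-corrected.
- A reader might infer inflated false positives. The calculations show none: overall error under the screen is at or slightly below 5%.
- A reader might take "Women with financial hardship are 4.64 times more likely to report lymphatic pain" (section 1.2), together with the collected "1-item for financial strain" (section 1.8), as proof that a strong predictor is being ignored. The figure is an association with reporting pain, and every woman enrolled already reports pain. It does not show that financial strain predicts the week-13 outcome among them.

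It is also fair that this is a pilot and that gains can be small. At 0.6 SD and 30 per arm, the gain is about 3 points over week 13 alone at r = 0.3, and about 5 points over the contrast at r = 0.7. At 0.3 SD every analysis is underpowered. Ethnicity adds at most about 1 point once baseline is in the model. It belongs there to respect the design.

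**Conclusion.** The concern holds. The plan states a rule, not merely a gap, and that rule selects covariates by chance after data by arm are seen. The rule bypasses the blocking factor, and the use of the baseline value is left undefined.

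The size depends on the reading. At 0.6 SD and 30 per arm, prespecified adjustment gains 3 to 26 points of power over week 13 alone (63% to 66/74/89%) and 17 to 5 points over the change contrast (49/63/84% to 66/74/89%). At 0.3 SD the gains are 1 to 14 points and 4 to 6 points, from the rounded figures. The harm is lost precision, plus slight conservatism under reading (a). These sizes rest on assumed effects and correlations and on a linear-model approximation, not on document figures. The plan should be changed before any data by arm are seen, because prespecification is not possible afterwards.

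**What to change.** In section 1.9.b, delete the significance-based rule and report baseline characteristics without tests.

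- **Continuous outcomes:** prespecify group, time, group-by-time, the week-0 value of that outcome and ethnicity. Either take week 0 out of the response vector, or keep it there with the arm means constrained equal in place of the covariate. Report the week-13 group difference with its confidence interval.
- **Complete pain reduction:** do not use week 0 as a response. Prespecify baseline BCLE-SEI lymphatic pain severity and ethnicity. Report a standardised (marginal) week-13 risk difference or odds ratio beside the unadjusted one, because the conditional odds ratio is a different quantity.
- **Other prognostic covariates:** name any before data by arm are seen.

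How a woman scoring 0 on the pain scale at baseline is counted is a separate endpoint-definition question.

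The cost is a rewritten analysis paragraph and two covariates per model. No new data are needed: the outcome measures are already taken at week 0, and ethnicity is already known for blocking. The downside is a null size of about 5–6% for the adjusted binary analysis, on the simulation that was not repeated.
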